9 CHANGES FROM THE PROTOCOL SPECIFIED STATISTICAL ANALYSIS

- Statistical analysis for the QSU-brief questionnaire data and the mCEQ questionnaire data will be performed including interaction terms for arm and time point to enable least square means to be calculated at each time point in order to explore the pattern of the CHTP 1.2 effect over time. The main comparison between arms will be the comparison over all of the time points.

Reason for change:

This analysis would capture the evolution of perception of the product and the adaptation process taking into account the subjects' repeated measurements.

- The descriptive statistics of the biomarkers of the primary endpoints will also be calculated per stratification factor.

Reason for change:

The protocol specified that primary endpoint analyses would be done by stratification factor, and this clarifies that descriptive statistics will also be presented by stratification factor.

- The summary of demographics will also be performed on the FAS.

Reason for change:

If the safety population differs from the FAS, then a summary of the demographics for the FAS is also required.

- The categorisation of the SES questionnaire into low, moderate and high SES will not be performed.

Reason for change:

There is no scoring algorithm available for the Socio-Economic Status questionnaire in the study population.

- The number and percentage of subjects with clinical findings will not be tabulated by sequence for laboratory parameters.

Reason for change:

No sequence occurred in this study. The tabulation will be done by arm. The error is corrected in this Analysis Plan.

- The endpoint "Ratio of 8-epi-prostaglandin F2 α (8-epi-PGF2 α) to prostaglandin F2 α (PGF2 α)" will only be listed.

Reason for change:

During the course of the study, the most recent development of the assay to measure the 8-epi-PGF2 α to PGF2 α ratio showed that the ratio is not an effective endpoint for the

determination of oxidative stress. The collection of samples and the analysis for this endpoint was stopped and the results will only be listed in the Clinical Study Report.

- The definition of the Quitters population was added in section **10.7 Quitters Population**.

Reason for change:

The purpose of this addition was to clarify the population on which exploratory endpoint 4 will be assessed.

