- ^l MCEQ: Day -2 to Day 5 on a daily basis, and on Visit 2, Visit 3 and Visit 4 (first day of the respective visits) for all subjects.
- ^m Cough Questionnaire to be done daily from Day -2 to Day 6 prior product use but no later than 11:30 AM. At Visit 2, Visit 3, and Visit 4 (second day of the respective visits) no later than 11:30 AM, irrespective of product use.
- ⁿ Samples will only be taken if additional consent for bio-banking is given by the subject.
- ^o Has to be done in at least 10 hours of fasting condition.
- ^p All examinations listed at the Day of Discharge (Day 6) will be conducted in subjects discontinuing the study.
- ^q The first and second day of each respective visit during the exposure period in the ambulatory setting.
- ^r Spontaneous reporting of new AEs/SAEs by the subject and active follow-up of ongoing AEs/SAEs by the site.

Confidentiality Statement

Data and information contained in this document are considered to constitute trade secrets and confidential commercial information, and the legal protections provided to such trade secrets and confidential information are hereby claimed under the provisions of applicable law. No part of this document may be publicly disclosed without the written consent of Philip Morris Products S.A.

Table A2 Schedule for 24-hour Urine Collection Assessments

Study Day	Baseline Period 24-hour Urine		Confinement Exposure Period 24-hour Urine					Ambulatory Exposure Period 24-hour-Urine		
	Day -2 (Day -2 to Day -1)	Day -1 (Day -1 to Day 1)	Day 1 (Day 1 to Day 2)	Day 2 (Day 2 to Day 3)	Day 3 (Day 3 to Day 4)	Day 4 (Day 4 to Day 5)	Day 5 (Day 5 to Day 6)	Visit 2 (First day to Second Day)	Visit 3 (First Day to Second Day)	Visit 4 (First Day to Second Day)
BoExp in urine ^a	•	•	•	•	•	•	•	•	•	•
Creatinine	•	•	•	•	•	•	•	•	•	•
11-DTX-B2, 8-epi-PGF _{2α} , 8-OHdG	•	•					•	•	•	•
Ames mutagenicity test		•					•			•
Bio-banking ^b		•					•			•

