The exposure period in confinement consists of 5 days of *ad libitum* use of the assigned product from 06:30 AM until around 11:00 PM each day in the CHTP 1.2 and CC arms.

Use of any tobacco/nicotine containing product other than the assigned product will not be allowed and may, at the discretion of the Principal Investigator (PI), result in the subject's discontinuation from the study.

Twenty four-hour urine will be collected from Day 1 to Day 5 on site ending in the morning of Day 6. On Day 1, product use must not start prior to the end of urine collection of Day -1. The end of the 24-hour urine collection period for Day 5 will end in the morning of Day 6 prior to Discharge.

Procedures on Day 6 will be conducted before discharge of the subject from the clinic after 9 days in a confined setting. Use of products will be allowed on Day 6 according to product allocation, but only after the sample for CYP2A6 activity has been taken, the cough assessment has been completed, and spirometry has been performed.

Subjects will be instructed to continue their assigned product/regimen in an ambulatory setting for 85 days.

- The Exposure Period in the Ambulatory Setting (from Discharge on Day 6 until Discharge at Day 90 Visit):

Subjects will be required to make three visits (Day 30 Visit, Day 60 Visit, and Day 90 Visit) to the investigational site. Each visit will cover 2 consecutive days on site.

For Day 30 Visit and Day 60 Visit, the subject will check-in in the morning on the first day of the respective visit and will check-out on the second day of the visit. For Day 90 Visit, the subject will check-in in the morning on the first day of the visit, and will be discharged on the second day of the visit after having performed all the safety examination procedures.

Twenty four-hour urine will be collected at each visit (Day 30 Visit, Day 60 Visit, and Day 90 Visit) at the site. The collection of 24-hour urine will start on the first day of the respective visits and will end 24 hours later on the following day. On the first day of Day 30 Visit, Day 60 Visit, and Day 90 Visit, subjects in the CHTP 1.2 and CC arms will be allowed to use their assigned product from the time of check-in until 11:00 PM. On the second day of Day 30 Visit and Day 60 Visit, product use will be allowed from 06:30 AM. The exposure period to the assigned IP will end at 11:00 PM on the first day of Day 90 Visit.

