7.4.3 Questionnaire of Smoking Urges-Brief (QSU-brief)

The QSU-brief (Cox et al. 2001) is a self-reported questionnaire completed daily from Day -2 to Day 5 between 08:00 PM and 11:00 PM, and at the first day of Day 30 Visit, Day 60 Visit and Day 90 Visit between 08:00 PM and 11:00 PM.

The QSU-brief consists of 10 items as presented in Table 3.

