12.5.2.1.3 NEQ

NEQ will be expressed as concentrations adjusted for creatinine and as the quantity excreted over 24 hours. It will be assumed that NEQ is log-normally distributed.

The values and percent changes for NEQ in the quantity excreted over 24-hours and the concentration adjusted for creatinine will be listed and summarized (Table 15.2.4.13.X and Listing 15.3.3.1). In addition line graphs will be produced for arm geometric means (and 95% CI) over all timepoints (Figure 15.1.2.26 and 15.1.2.27).

The analysis will compare the log-transformed NEQ between the CHTP 1.2 and CC arms on Day 5 and Day 90 Visit. The statistical model and SAS code will be the same as described in Section 12.5.1.1 “Primary endpoints” (Table 15.2.4.1).

In addition, a repeated measures mixed model on the log-transformed NEQ will be used with terms for log-transformed baseline, sex, average daily CC consumption over the last 6 weeks as reported during admission, arm, timepoint, and the interaction between arm and timepoint. The interaction term will be removed if $p > 0.1$.

The SAS code to be used is shown below:

```
Proc mixed data=_data_ method=REML;
Class arm sex cigarette_cons time_point_cat subject period;
Model log(NEQ) = log(base) sex period cigarette_cons arm
arm*time_point time_point;
Repeated time_point_cat / subject=subject type=un;
Lsmean arm / diff alpha=0.05 cl;
Run;
```

The least squares (LS) means and estimate of the difference along with its 95% CI will be back-transformed before presenting in the tables. The geometric LS means for each arm along with the reduction (i.e: 100% - ratio of CHTP 1.2 : CC (%)) and 95% CI will be presented in Table 15.2.4.14. This will be done for all individual timepoints. If the interaction term is present in the model, the reduction will also be shown for the individual timepoints.

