12.5.3.1.1 Urge-to-Smoke Questionnaire of Smoking Urges Brief

All summaries, profiles and analysis will be presented for the CHTP 1.2 and CC arms.

The change from baseline will be calculated for the total score and the two domain scores (relief and reward). The total score and two domain scores, along with the change from baseline will be summarized (Table 15.2.5.1). The answers to the individual questions, along with the domain scores, total scores and changes from baseline will be listed (Listing 15.3.5.1).

The profiles of the arithmetic means and LS Mean differences per timepoint for the total score and two domain scores will be produced (Figure 15.1.3.1 and Figure 15.1.3.2).

The analysis will compare each post baseline timepoint in the domain and total scores. A repeated measures mixed model will be used with terms for baseline QSU-BRIEF score, sex, average daily CC consumption over the last 6 weeks as reported during admission, arm, timepoint, and the interaction between arm and timepoint. The interaction term will be removed if $p > 0.1$.

The SAS code will be the same as the repeated measures model described in Section “12.5.1.1 Primary endpoints”.

LS means for each arm along with the difference (CHTP 1.2 - CC) with 95% CI will be presented in table 15.2.5.2.

All figures, summaries and analyses will be performed on the Per Protocol Populations.

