15.2.4.14	Analysis of NEQ over the exposure period – Per Protocol Population
15.2.4.15	Descriptive Statistics of Plasma Cotinine and Nicotine Concentrations (ng/mL) – Per Protocol Population
15.2.4.16	Analysis of Plasma Cotinine and Nicotine Concentrations over the exposure period – Per Protocol Population
15.2.4.17	Descriptive Statistics of CYP1A2 Activity (%) – Per Protocol Population
15.2.4.18	Analysis of CYP1A2 Activity (%) – Per Protocol Population
15.2.4.19.1	Descriptive Statistics of Spirometry Results – Safety Population
15.2.4.19.2	Descriptive Statistics of Spirometry Results – Per Protocol Population
15.2.4.20.1	Spirometry Interpretation of Clinical Relevance Shift from Baseline- Safety Population
15.2.4.20.2	Spirometry Interpretation of Clinical Relevance Shift from Baseline- Per-Protocol Population
15.2.4.21	Analysis of Spirometry Results – Per Protocol Population
15.2.4.22.1	Summary of Cough Assessments Over Study by Arm – Safety Population
15.2.4.22.2	Summary of Cough Assessments Over Study by Arm – Per Protocol Population
15.2.4.23.1	Summary of Cough Assessments During the Ambulatory Period by Product Use Time Periods – Safety Population
15.2.4.23.2	Summary of Cough Assessments During the Ambulatory Period by Product Use Time Periods – Per Protocol Population
15.2.4.24.1	Summary of Cough Assessments by Arm and Study Day – Safety Population
15.2.4.24.2	Summary of Cough Assessments by Arm and Study Day – Per Protocol Population
15.2.4.25.1	Analysis of Cough during the Confinement Period – Safety Population
15.2.4.25.2	Analysis of Cough during the Confinement Period – Per Protocol Population
15.2.4.26.1	Analysis of Cough during the Ambulatory Period – Safety Population
15.2.4.26.2	Analysis of Cough during the Ambulatory Period – Per Protocol Population
15.2.4.27	Descriptive Statistics of Cardiovascular Risk Endpoints – Per Protocol Population

Tables	Title
15.2.4.28	Analysis of Cardiovascular Risk Endpoints – Per Protocol Population
15.2.4.29	Descriptive Statistics of Risk Endpoints related to Oxidative Stress– Per Protocol Population
15.2.4.30	Analysis of Risk Endpoints related to Oxidative Stress– Per Protocol Population
15.2.5.1	Descriptive Statistics of Questionnaire on Smoking Urges-brief Total and Factor Scores – Per Protocol Population
15.2.5.2	Analysis of Questionnaire on Smoking Urges -brief Factors and Total Scores – Per Protocol Population

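### The overall QSU-brief, mCEQ, NEQ and nicotine/cotinine contrasts have no stated weights and, at equal weights, rest mostly on confinement; report confinement and ambulatory contrasts beside them

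*SAP*

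**What the plan says.** SAP section 9 adds an arm-by-timepoint interaction to the QSU-brief and mCEQ models so that least-squares means are available at each timepoint. It then states: "The main comparison between arms will be the comparison over all of the time points". Sections 12.5.3.1.1 and 12.5.3.1.2 specify these models; for QSU-brief, "The analysis will compare each post baseline timepoint in the domain and total scores". Both sections drop the interaction when p exceeds 0.1.

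For NEQ, section 12.5.2.1.3 plans ANCOVAs at Day 5 and Day 90 and adds a repeated-measures model with the same interaction rule. Section 12.5.2.2 applies that model to plasma nicotine and cotinine. The only least-squares-means request in the printed code is "Lsmean arm / diff alpha=0.05 cl", and the NEQ output is titled "Analysis of NEQ over the exposure period – Per Protocol Population". NEQ reductions at single timepoints appear only if the interaction stays.

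The schedule is dense early and sparse later:
- QSU-brief is a "self-reported questionnaire completed daily from Day -2 to Day 5 between 08:00 PM and 11:00 PM", repeated at the Day 30, 60 and 90 Visits (SAP 7.4.3).
- The protocol's Appendix A gives "MCEQ: Day -2 to Day 5 on a daily basis, and on Visit 2, Visit 3 and Visit 4".
- For urine, SAP 6.1 has "Twenty four-hour urine will be collected from Day 1 to Day 5 on site ending in the morning of Day 6", then one collection per ambulatory visit.
- Plasma nicotine/cotinine has an extra Day 6 morning sample (SAP Table 14).

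Two details of the code matter. CLASS lists `time_point_cat`, but MODEL uses `time_point`. Section 12.5.3.1.1 refers QSU-brief to a repeated-measures model in section 12.5.1.1, which contains only a single-timepoint ANCOVA.

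**The concern.** An average over scheduled assessments is not an average over exposure. Five of the eight post-baseline assessments fall in the first five days, when product is handed out stick by stick and some subjects are new to it. The remaining 85 days contribute three.

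The SAP expects the arm effect to change: section 9 justifies the model as a way to follow adaptation to the product, and section 6.3.3.1 anticipates dual use after discharge. For cough, section 12.5.2.5 already models the two settings separately. For these four outcomes it pools them without saying how.

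The stake is interpretation. A mostly first-week average, in a table titled as covering the exposure period, may be read as a 90-day effect. Equally, an effect that appears only after discharge would be diluted.

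**Working it through.** The documents give no weighting figure, so there is none to reproduce.

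**Counts.** Baseline is the last valid value before exposure (SAP Table 17), so Days -2 and -1 do not enter the average.
- QSU-brief, mCEQ, NEQ: Days 1–5 plus Days 30, 60, 90 = 8 timepoints, 5 in confinement.
- Nicotine/cotinine: Days 1–5, Day 6 morning, and Days 30, 60, 90 = 9 timepoints, 6 in confinement.
- Exposure (SAP 6.1): 5 days in confinement plus 85 ambulatory = 90.

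**Equal weights.** With class time and the interaction kept, the arm contrast weights each of k timepoints by 1/k.
- 8 timepoints: 5/8 = 62.5% confinement.
- 9 timepoints: 6/9 = 66.7% confinement.
- Exposure share: 5/90 = 5.6%. With the ±5-day window on Visit 4 it lies between 5/95 = 5.3% and 5/85 = 5.9%.

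**When those conditions fail.** The weights then come from generalised least squares and depend on the covariance and on missing data. The documents give no covariance, so three were assumed. Each was run with complete data (80 and 40 subjects, SAP section 8) and with half of the CHTP 1.2 arm absent from the ambulatory per-protocol (PP) sets, the limit of the retention assumed in section 8. The continuous-time column takes `time_point` as study day and keeps `period` in the model.

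Confinement share, 8 timepoints, complete data / 50% loss:

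| Assumed covariance | Class time, interaction kept | Class time, interaction dropped | `time_point` continuous, as printed |
|---|---|---|---|
| Common correlation 0.5 | 62.5% / 62.5% | 62.5% / 71.4% | 62.5% / 71.4% |
| Correlation 0.8 in confinement, 0.4 across settings, 0.5 ambulatory | 62.5% / 62.5% | 37.7% / 49.2% | 51.5% / 62.0% |
| Correlation 0.6, 0.3, 0.6; ambulatory SD ×1.5 | 62.5% / 62.5% | 83.9% / 87.8% | 72.6% / 79.1% |

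For nicotine/cotinine the same runs give 66.7% with the interaction kept, 38.1% to 88.4% with it dropped, and 53.9% to 81.3% as printed.

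As printed, the arm contrast is evaluated at the mean of `time_point`, not averaged over timepoints. For 8 timepoints with complete data that is (1+2+3+4+5+30+60+90)/8 = Day 24.4. With 50% loss it is (120×15 + 80×180)/(120×5 + 80×3) = 16,200/840 = Day 19.3.

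**What the weights can do (assumed effects, for illustration only).**
- A difference of 1.0 in confinement and 0.2 afterwards: 0.625×1.0 + 0.375×0.2 = 0.70 at equal weights, against 0.056×1.0 + 0.944×0.2 = 0.24 by exposure days.
- The reverse pattern: 0.625×0.2 + 0.375×1.0 = 0.50, against 0.056×0.2 + 0.944×1.0 = 0.96.
- NEQ ratios of 0.80 then 1.00, averaged on the log scale: exp(0.625×ln 0.80) = 0.87, against exp(0.056×ln 0.80) = 0.99.

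**The case against.** The strongest reply is that the reader will not depend on the pooled figure. Section 9 includes the interaction so that the time pattern can be seen. Sections 12.5.3.1.1 and 12.5.3.1.2 compare every post-baseline timepoint, and Figures 15.1.3.2 and 15.1.3.4 plot least-squares mean differences. An early-only NEQ effect would show in the Day 5 and Day 90 ANCOVAs. QSU-brief and mCEQ are exploratory, NEQ and nicotine/cotinine secondary, and none is in the topline (13.2) or registry (13.4) tables. If the interaction is dropped, the model assumes one common arm effect, so the weights matter less.

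Most of this stands and limits the point to an improvement. It does not dispose of it. A p-value above 0.1 does not show a common effect, yet it removes the separate NEQ reductions and makes the fitted arm difference identical at every QSU-brief and mCEQ timepoint. The printed code requests no per-timepoint means. Per-timepoint output also does not tell the reader what the comparison named as main is averaging.

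A reader might go further and conclude that the Day 30/60/90 mean, or a time-weighted mean, should become the main estimate. The documents do not support that. The early days belong to a comparison meant to follow adaptation. The ambulatory PP sets are the most selected data. Time weighting is also not unique: a trapezoid over the sampled days gives Days 1–5 a share of (0.5+1+1+1+13)/89 = 18.5%, not 5.6%. Nor is the contrast simply enforced against free use: Table 12 treats more than 2 CC in a day, or an average above 0.5 CC per day, as ambulatory non-compliance in the CHTP 1.2 arm.

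**Conclusion.** The point holds as a matter of specification and labelling. At equal weights, confinement supplies 62.5% of the overall contrast for QSU-brief, mCEQ and NEQ and 66.7% for nicotine/cotinine, from 5.6% of exposure days. These shares rest on class time and a retained interaction. Otherwise the plan does not fix them, and the ranges above rest on assumed covariances.

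Three stronger readings do not hold. First, 62.5% is not a fixed property of the SAP, and it does not apply to nicotine/cotinine. Second, the overall contrast is named as main only for QSU-brief and mCEQ; the NEQ repeated model supplements its two ANCOVAs. Third, pooling does not contradict the QSU-brief and mCEQ objective, which is descriptive and lists assessments from Day 1 to Day 90; the wording about the whole exposure period belongs to the nicotine objective (SAP 5.2, objective 4). Nothing in the documents shows that the arm effects actually differ between settings.

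**What to change.** In SAP sections 9, 12.5.2.1.3, 12.5.2.2, 12.5.3.1.1 and 12.5.3.1.2:

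1. Prespecify two contrasts beside the overall one: the mean of the confinement timepoints and the mean of Days 30, 60 and 90. Take all three from the model with the interaction kept, whatever its p-value. The overall contrast is then exactly 5/8 of the first plus 3/8 of the second (6/9 and 3/9 for nicotine/cotinine), on the log scale for the log-transformed outcomes.
2. Describe the overall contrast as an equal-weight average over scheduled assessments, not as the effect over the 90-day exposure.
3. Put `time_point` in CLASS, or use `time_point_cat` in MODEL. Then remove `period` from MODEL: it becomes a function of timepoint and can leave the arm least-squares means non-estimable, although the arm difference is unaffected.
4. Point the QSU-brief code reference to section 12.5.2.1.3.

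The ambulatory mean need not become the main estimate. The cost is SAP wording, an ESTIMATE or LSMESTIMATE statement per model for the added contrasts, and a little more output; no new data are needed. The ambulatory contrast will have a wider confidence interval. It rests on three visits and on PP sets in which the plan counts on keeping only half or more of the CHTP 1.2 arm, so it should be read with that selection in mind.

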10 ANALYSIS POPULATIONS

The study population characteristics will be described on the Safety Population, FAS, (if different from Safety Population), and on the Per-Protocol populations for Period 1 and 4. The per-protocol populations will be the primary analysis set for biomarkers of exposure, cotinine and nicotine in plasma, CYP1A2, CYP2A6, Ames Mutagenicity test, clinical risk endpoints, FTND, mCEQ, ITUQ, Cough and QSU-brief. The Full Analysis Set will be the primary analysis set for exposure to product, compliance to randomization arm, Prochaska and SES. Exposure and questionnaires, as a secondary analysis, will be described by randomization arm and product use category using the full analysis set. If the FAS and PP population differ, the biomarkers of exposure tables will be repeated on the FAS.

Safety will be analyzed using the safety population.

